Eligibility criteria	
Inclusion Criteria (Major Criteria):
 
(1) $18 \leq \text{age} \leq 80$ years, Gender is not limited;(2) Patients diagnosed clinically as benign or malignant intracranial tumors, as well as malignant solid tumors in the head and neck, chest, abdomen, spine, pelvic cavity, and limbs, based on cellular or histopathological diagnosis and/or evidence from imaging, laboratory tests, etc. (recurrent patients may only have evidence from imaging, laboratory tests, etc.);(3) The target lesion is a measurable solid tumor, and the longest diameter of the lesion should be ≥ 10mm;(5) According to the researchers' assessment, the expected survival time exceeds 6 months;(6) ECOG physical condition is graded as 0 to 2;(7) Women of childbearing had negative results in the blood pregnancy test (Human Chorionic Gonadotropin, HCG) 7 days prior to the first treatment;(8) The subject or subject's guardian is able to understand the purpose of the study, demonstrate sufficient compliance with the protocol and sign informed consent form.
Specifications for the use of investigational medical device	
Exclusion Criteria (Major Criteria):
 
(1) The subject with radiotherapy contraindications, including the known genetic tendencies that increase the sensitivity of normal tissue radiotherapy or the accompanying diseases that lead to hypersensitivity to radiotherapy;(2) The subject with other uncontrolled tumors except that to be treated according to medical history or the investigator's estimation, or with other malignant tumors within five years prior to enrollment;(3) Implanted pacemakers or other metal prosthesis within the scope of proton therapy;(4) Other situations that investigator determines not suitable for enrollment.

Statistical analysis with SAS 9.4 software.

All data are described statistically, including baseline data, all efficacy measures, and all safety data. The measurement data give the mean, standard deviation, minimum, maximum, median, 25th quantile and 75th quantile; The counting data gives the frequency and composition ratio.

Effectiveness analysis

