3.1.4 Effectiveness evaluation methods

If it is not possible to follow up at the clinical trial center according to the visit arrangement due to the epidemic, the clinical examination can be examined by other tertiary hospitals, and the test results will be transmitted back to the clinical trial center for evaluation; The carrier of imaging data in the outer hospital is not limited, and it is necessary to ensure that the imaging department of the center can be opened and read.

3.1.4.1 The main effectiveness evaluation indicators and the methods and time selection of their evaluation, recording and analysis

(1) Tumor disease control rate (DCR).

Reason for selection: According to the clinical trial effectiveness evaluation in the "Guidelines for the Review of Clinical Evaluation Technologies of Proton Carbon Ion Therapy System" (CFDA Circular No. 4 [2018]): "In view of the local characteristics of radiotherapy, it is recommended that the efficacy evaluation should be based on local control, and according to

the different diseases, the common standards in clinical research, such as the efficacy evaluation criteria for solid tumors, should be reasonably adopted RECIST. The efficacy evaluation can be divided into complete response CR, partial response PR, disease stable SD, disease progression PD, and the effective definition is: "CR+PR+SD.""; Due to the particularity of the disease, the evaluation method recommended in the relevant diagnosis and treatment guidelines is selected. The tumor disease control rate was selected as the main effectiveness evaluation index, which was relatively objective and reproducible, and adopted the common standard in clinical research, which was widely recognized and applied by clinicians.

Definition of indicators: the occurrence of CR, PR and SD after the end of treatment is disease control; No biochemical recurrence at the end of prostate cancer treatment, no regional lymph nodes or distant metastases, considered disease control. Proportion of participants who developed disease control three months after the end of the last radiotherapy.

Metric type: Qualitative.

Data collection time: screening period, 3 months \pm 7 days after the end of the last treatment.

Evaluation time: 3 months \pm 7 days after the end of the last treatment.

Site of evaluation: Tumor receiving radiation therapy.

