Evaluation method: The changes in tumor CT or MRI imaging before and after treatment were evaluated by an independent imaging review panel according to RECIST 1.1. At 3 months of radiographic evaluation, if PD is found, PET-CT is required to confirm it.

Calculation formula: DCR = number of disease control subjects / total number of subjects \times 100%.

Criteria: See RECIST 1.1 for details. At the time of 3-month imaging evaluation, if the patient is found to have PD, PET-CT examination is required to confirm it, if progress is confirmed, it is recorded as PD, if progress cannot be confirmed, it may

be false progression, and it is recorded as SD. If prostate cancer does not have biochemical recurrence, PET-CT examination is not required, and there is no metastasis by default, which is regarded as tumor control, and if biochemical recurrence occurs, it is regarded as tumor not controlled, and PET-CT is required to confirm tumor metastasis.

Note: Participants who aborted the trial for any reason (except loss to follow-up) before the end of the last radiation therapy were considered to have disease progression (PD) or were not controlled. Disease site evaluation uses the same approach as baseline, including consistent contrasted/non-contrast scans and prompt scanning. If changes are needed, the case must be discussed with a radiologist to determine whether an alternative approach is possible. If not, the objective situation in the future is unclear.

3.1.4.2 Secondary effectiveness evaluation indicators and their methods and timing of evaluation, recording, analysis

(1) Objective response rate (ORR).

Reason for selection: The Guidelines for the Review of Clinical Evaluation Technologies of Proton Carbon Ion Therapy Systems (CFDA Circular No. 4 [2018]) recommends the use of the latest version of the commonly used evaluation criteria for radiation oncology as the clinical trial evaluation criteria, so RECIST 1.1 is used. Relevant indicators as effectiveness evaluation criteria; Due to the particularity of the disease, the evaluation method recommended in the relevant diagnosis and treatment guidelines is selected. All of them can directly measure the effect of radiotherapy and are widely recognized and applied by clinicians.

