Definition of indicators: CR or PR after the end of treatment is considered objective remission, prostate cancer has no biochemical recurrence at the end of the last treatment, and no regional lymph nodes or distant metastasis are considered objective remission. Proportion of participants who experienced objective remission at each time point after the end of the last treatment.

Metric type: Qualitative.

Data collection time: screen period, 3 days, 1 month \pm 7 days, 2 months, \pm 7 days, 3 months, \pm 7 days after the end of the last treatment.

Evaluation time: 3 days, 1 month \pm 7 days, 2 months, \pm 7 days, 3 months, \pm 7 days after the last treatment.

Site of evaluation: Tumor receiving radiation therapy.

Evaluation method: The changes in tumor CT or MRI imaging before and after treatment were evaluated by an independent imaging review panel according to RECIST 1.1. At 3 months of radiographic evaluation, if PD is found, PET-CT is required to confirm it.

Calculation formula: ORR = number of subjects in objective response / total number of subjects \times 100%.

Criteria: See RECIST 1.1 for details. At the time of 3-month imaging evaluation, if the patient is found to have PD, PET-CT examination is required to confirm it, if progress is confirmed, it is recorded as PD, if progress cannot be confirmed, it may be false progression, and it is recorded as SD. If prostate cancer does not have biochemical recurrence, PET-CT examination is not required, and there is no metastasis by default, which is regarded as objective remission, and if biochemical recurrence occurs, it is regarded as not objectively remission, and PET-CT is required to confirm tumor metastasis.

Note: Participants who aborted the trial for any reason (other than loss to follow-up) before the end of the last radiotherapy were considered to have not responded objectively. Disease site evaluation uses the same approach as baseline, including consistent contrasted/non-contrast scans and prompt scanning. If changes are needed, the case must be discussed with a radiologist to determine whether an alternative approach is possible. If not, the objective situation in the future is unclear.

(2) Tumor disease control rate (DCR).

Reason for selection: DCR 3 months after the end of the last treatment was the primary evaluation index, and DCR at other follow-up time was used as a secondary evaluation index.

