2.1.2 Secondary effectiveness measures

- **Objective response rate (ORR)**

CR or PR was considered objective remission at the end of treatment, no biochemical recurrence occurred at the end of prostate cancer at the end of treatment, and no regional lymph node metastasis or distant metastasis was considered objective remission. Proportion of subjects with objective remission at each time point after the end of the last treatment.

Calculation formula: $ORR = \text{number of subjects with objective remission} / \text{total number of subjects} \times 100\%$

- **Tumor disease control rate (DCR) at 1 month after the end of last treatment**

The occurrence of CR, PR and SD after the end of treatment was considered to be disease control, and the absence of biochemical recurrence at the end of treatment of prostate cancer was considered to be disease control. Proportion of subjects with disease control 1 month after the end of the last treatment.

Calculation formula: $DCR = \text{number of subjects under disease control} / \text{total number of subjects} \times$

100%

- **Tumor markers (if required)**

Tumor marker examination was performed and clinically significant changes in tumor markers (before and after radiation therapy) were reported at the discretion of the investigator.

- **Ease of use (ProBeam System, Radiation Therapy Management Software (Aria), Radiation Therapy Planning Software (Eclipse))**

Investigators using the corresponding functions scored according to the Likert scale and collected open-ended questions to evaluate the comprehensive feeling of ease of use during the treatment.

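### ORR counts prostate patients as responders for absence of recurrence, so RECIST stable disease can be scored as response

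*Protocol*

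**What the plan says.** **General ORR rule.** Protocol 3.1.4.2(1): "CR or PR after the end of treatment is considered objective remission". Stable disease does not count.

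**Prostate ORR rule.** The same definition continues that, for prostate cancer without biochemical recurrence, "no regional lymph nodes or distant metastasis are considered objective remission". The criteria paragraph of that section then says that, without biochemical recurrence, PET-CT is not needed and "there is no metastasis by default, which is regarded as objective remission". SAP 2.1.2 keeps the rule: "no regional lymph node metastasis or distant metastasis was considered objective remission".

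**General DCR rule.** Protocol 3.1.4.1(1): "the occurrence of CR, PR and SD after the end of treatment is disease control".

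**Prostate DCR rule.** Protocol 3.1.4.1(1): "No biochemical recurrence at the end of prostate cancer treatment, no regional lymph nodes or distant metastases, considered disease control". Its criteria paragraph has the same default, with a different label: "there is no metastasis by default, which is regarded as tumor control". SAP 2.1.1 and 2.1.2 require only absence of biochemical recurrence for prostate DCR.

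**Assessability.** Inclusion criterion (3) in the Protocol summary reads "The target lesion is a measurable solid tumor, and the longest diameter of the lesion should be" at least 10 mm. Protocol 3.1.4.2(1) has the independent panel read CT or MRI by RECIST 1.1, with ORR evaluated at 3 days and at 1, 2 and 3 months after the last treatment.

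**Analysis.** ORR is reported with a Clopper-Pearson 95% interval (Protocol 4.7.1, SAP 5.4.2), on FAS and PPS, without a target value.

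**The concern.** Absence of biochemical recurrence means that failure has not been seen. It does not mean that the tumour has shrunk. CR and PR are statements about shrinkage, and separating them from SD is the reason for reporting ORR alongside DCR. For prostate patients the plan removes that separation.

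ORR is the first-listed secondary efficacy endpoint. A pooled rate that uses a response rule at most sites and a non-failure rule at one has no single meaning, and its value depends on how many prostate patients are enrolled. A reader of the report who sees ORR described as CR or PR would take it as a RECIST rate. Duration of response, which SAP 5.4.2 also describes, could inherit the same cases.

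**Working it through.** **1. The plan's own figures.** The only design figures are for DCR. Inputs are a target of 80%, an expected rate of 95%, two-sided alpha 0.05 and power 80% (Protocol 3.1.2, 4.2.1, 4.3), with 10% dropout (4.4).

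n = [(1.96 × √(0.80 × 0.20) + 0.8416 × √(0.95 × 0.05)) / 0.15]² = 41.6, rounded up to 42.

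42 / 0.9 = 46.7, rounded up to 47.

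Both figures reproduce. Neither involves ORR, so changing the ORR rule leaves them as they are.

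**2. How individual patients are scored.**

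- *RECIST SD, no biochemical recurrence, no metastasis.* A prostate patient is controlled and a responder under both documents. A patient with SD at any other site is controlled but not a responder.
- *No biochemical recurrence, but metastasis known.* In the Protocol, the prostate wording for ORR and DCR is the same, so both indicators take the same value however the default is read. In the SAP, the patient meets the prostate DCR rule but not the ORR rule.
- *RECIST CR or PR with biochemical recurrence.* The Protocol scores this prostate patient as a non-responder, which is an error in the opposite direction.

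The prostate rules for ORR and DCR are therefore identical in the Protocol. In the SAP they differ only by the nodal and distant metastasis condition, and no tumour change is required in either document.

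**3. Size of the shift.** Let k be the number of prostate patients without recurrence (under the SAP wording, also without metastasis), q the proportion of them with RECIST CR or PR, and N the analysis-set size. The plan counts k responders among them and RECIST would count kq, so

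shift in ORR = (k − kq)/N = k(1 − q)/N,

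less any prostate patients with CR/PR and biochemical recurrence, divided by N.

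The documents give neither k nor q. The Protocol summary asks for seven site groups as evenly filled as possible, and 47/7 = 6.7, so about 7 pelvic cases. Treating all of them as prostate is an assumption. With N = 47:

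| k (assumed) | q = 60% | q = 20% |
|---|---|---|
| 0 | 0 | 0 |
| 1 | 0.9 points | 1.7 points |
| 3 | 2.6 points | 5.1 points |
| 7 | 6.0 points | 11.9 points |
| 14 | 11.9 points | 23.8 points |

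For k = 7: 7 × 0.4/47 = 6.0% and 7 × 0.8/47 = 11.9%. If N is the 42 evaluable subjects, the same k gives 7 × 0.4/42 = 6.7 and 7 × 0.8/42 = 13.3 points.

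**4. Effect on the reported interval.** Assume N = 47, k = 7, and a true ORR of 40% both overall and in the prostate patients. The expected shift is 7 × 0.6/47 = 8.9 points. In whole patients, ORR moves from 19/47 (40.4%, 95% CI 26.4 to 55.7) to about 23/47 (48.9%, 95% CI 34.1 to 63.9).

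**The case against.** The strongest reply is that the rule is deliberate and prespecified. Protocol 3.1.4.2(1) says that, because of the particular nature of the disease, the method recommended in the relevant treatment guidelines is used. Those guidelines are not available here, so whether they support a PSA-based response definition cannot be checked. That reason can support a disease-specific way of judging control. It does not explain why the same non-failure state also counts as response, in an endpoint that the section justifies by RECIST 1.1.

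Four stronger readings are tempting, and the documents do not support them:

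- *ORR equals DCR for prostate throughout the plan.* This is true of the Protocol only. SAP 2.1.2 keeps a metastasis condition for ORR that the SAP drops for DCR.
- *The inflation has a known size or ceiling.* Seven prostate patients with no true responders would give 7/47 = 14.9 points, but even spread over sites is only an aim, so 7 is not a cap. At the other end, the inclusion criteria do not name prostate cancer, and the shift may be zero.
- *ORR will contradict the waterfall plot.* The plot shows each subject's largest reduction in the sum of diameters, which is a different measure. It partly mitigates the problem because it displays actual shrinkage.
- *The bias can only be upward.* A patient with CR/PR and biochemical recurrence is counted as a non-responder. This effect is probably small, but it exists.

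It also stands that PPS is restricted to subjects with a measurable baseline lesion (Protocol 4.9, SAP 3). The plan thus allows for some FAS subjects without one, despite the inclusion criterion, and a RECIST-only rule must say how to score them.

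**Conclusion.** The point holds as a flaw in a secondary endpoint's definition. In both documents a prostate patient with RECIST stable disease can be counted as an objective responder, so ORR mixes response with non-progression and is expected to be too high. The textual reading is firm. The amount is not known: it is zero without prostate patients, or if all of them have CR/PR, and 6.0 to 11.9 points under the assumed k = 7, N = 47 and q from 60% to 20%.

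A reader might infer that the trial's conclusion is at risk. It is not, on this point. Protocol 4.5 decides success on DCR and CTCAE toxicity, ORR carries no target or test, and the sample size does not depend on it. The correction should be made, but it does not bear on whether the trial passes.

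**What to change.** In both Protocol 3.1.4.2(1) and SAP 2.1.2, derive ORR as RECIST 1.1 CR or PR of the irradiated lesion for all subjects, prostate cancer included. State that a subject without a measurable baseline lesion counts as a non-responder in FAS. Report biochemical control as a separate prostate-only line. If the sponsor keeps the PSA-based rule, also report ORR with prostate patients excluded from numerator and denominator.

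Cost: wording changes in the Protocol and the SAP, and one changed derivation. The CT or MRI reads by the panel are already planned at every ORR time point, so no scans are added. The downside for the sponsor is that the reported ORR may be lower.

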3.1.5 Safety evaluation methods

If it is not possible to follow up at the clinical trial center according to the visit arrangement due to the epidemic, the clinical examination can be examined by other tertiary hospitals, and the test results will be transmitted back to the clinical trial center for evaluation; The carrier of imaging data in the outer hospital is not limited, and it is necessary to ensure that the imaging department of the center can be opened and read.

3.1.5.1 The main safety evaluation indicators and the methods and time selection of their evaluation, recording and analysis

(1) CTCAE 3 toxicity ratio

Reason for selection: According to the Guidelines for the Technical Review of Clinical Evaluation of Proton Carbon Ion Therapy System (CFDA Circular No. 4 of 2018), if the proportion of CTCAE grade 3 acute toxic reactions exceeds 5%, it is considered as a clinical trial failure, so it is selected. The proportion of CTCAE grade 3 toxicity is used as the main safety evaluation index, and CTCAE is a commonly used safety evaluation standard in radiation oncology, which is widely recognized and applied by clinicians.

Indicator definition: Proportion of subjects with grade 3 toxicity during the trial cycle.

Metric type: Qualitative.

Data collection time: the entire clinical trial cycle.

Evaluation time: 3 months \pm 7 days after the last treatment.

Evaluation methodology: Investigators recorded AEs that occurred during the clinical trial cycle and graded them according to CTCAE V5.0.

Calculation formula: proportion of CTCAE grade 3 toxicities = (number of subjects with CTCAE grade 3 toxicity in the test cycle) / total number of subjects \times 100%.

Judging criteria: See CTCAE V5.0 for details.

(2) CTCAE Grade 4 and 5 toxicity ratio

Reason for selection: According to the Guidelines for the Review of Clinical Evaluation Technologies of Proton Carbon Ion Therapy System (CFDA Circular No. 4 of 2018), CTCAE grade 4 and 5 toxicities are considered to be clinical trial failures, so 4 is selected. The proportion of grade 4 and grade 5 toxicity reactions is used as a safety evaluation index, and CTCAE is a commonly used safety evaluation standard in radiation oncology, which is widely recognized and applied by clinicians.

Indicator definition: Proportion of subjects with toxicity of grade 4 and 5 during the trial cycle.

Metric type: Qualitative.

Data collection time: the entire clinical trial cycle.

Evaluation time: 3 months \pm 7 days after the last treatment.

Evaluation methodology: Investigators recorded AEs that occurred during the clinical trial cycle and graded them according to CTCAE V5.0.

Formula: Proportion of CTCAE grade 4 and 5 toxicities = (number of subjects with CTCAE grade 4 and 5 reactions in the test cycle) / total number of subjects × 100%

Judging criteria: See CTCAE V5.0 for details.

3.1.5.2 Secondary safety evaluation indicators and their methods and time selection for evaluation, recording and analysis

(1) CTCAE grade 1 and 2 toxicity ratio

Reason for selection: The proportion of CTCAE grade 3~5 toxicity reactions 3 months after the end of the last treatment was the main safety evaluation index, and the proportion of CTCAE grade 1 and grade 2 toxicity reactions was used as a secondary safety evaluation index for auxiliary evaluation.

Indicator definition: Proportion of subjects with grade 1 and 2 toxicity during the trial cycle.

Metric type: Qualitative.

Data collection time: the entire clinical trial cycle.

Evaluation time: 3 months ± 7 days after the last treatment.

Evaluation methodology: Investigators recorded AEs that occurred during the clinical trial cycle and graded them according to CTCAE V5.0.

Calculation formula: proportion of CTCAE grade 1 and 2 toxicities = (number of subjects with CTCAE grade 1 and 2 toxicities in the test cycle) / Total number of participants × 100%.

Judging criteria: See CTCAE V5.0 for details.

(2) Laboratory tests

Reason for selection: According to the Guidelines for Technical Review of Clinical Evaluation of Proton Carbon Ion Therapy System (CFDA Circular No. 4 of 2018), changes in clinical symptoms and signs should be recorded for clinical manifestations, tumor improvement (imaging examinations, laboratory test data), etc., and comprehensive analysis should be carried out. At the same time, it is a routine safety monitoring index for medical device clinical trials.

Data collection and evaluation time: screening period, treatment period 1st day per week (Monday to Sunday is regarded as 1 calendar week, each natural week on the day of the first treatment), before treatment or -1 day (blood count only), 3 days after the end of the last treatment, 1 month \pm 7 days (except coagulation routine), 2 months \pm 7 days (except coagulation routine), 3 months, \pm 7 days (except coagulation routine). .

Evaluation items: blood routine, coagulation routine, urine routine, liver function, kidney function.

Evaluation method: Laboratory tests are performed and the investigator judges clinically significant changes in laboratory indicators (before and after radiotherapy).

(3) ECOG grading of physical status

Reason for selection: According to the Guidelines for the Review of Clinical Evaluation Technologies of Proton Carbon Ion Therapy System (CFDA Circular No. 4 of 2018), the follow-up of subjects should include safety and efficacy evaluation. The general condition of the subjects is recommended to be evaluated using the internationally accepted scoring method.

Data collection time and evaluation time: screening period, treatment period on the first day of each week (every Monday to Sunday is regarded as 1 calendar week, each natural week on the day of the first treatment) before treatment or -1 day, 3 days after the end of the last treatment, 1 month \pm 7 days, 2 months \pm 7 days, 3 months, \pm 7 days.

Evaluation method: ECOG physical performance status was graded and reported by the investigator to report clinically significant changes in the test results (before and after radiotherapy).

(4) Adverse event rate

Reason for selection: Routine safety monitoring indicators for clinical trials of medical devices.

Indicator definition: Adverse events are adverse medical events that occur during clinical trials, whether or not related to a device.

Metric type: Qualitative.

Data collection time: the entire clinical trial cycle.

Evaluation time: 3 months \pm 7 days after the last treatment.

Evaluation method: The investigator recorded all AEs that occurred.

Calculation formula: adverse event rate = number of subjects with adverse events in this group / total number of subjects in this group \times 100%.

(5) Serious adverse event rate

Reason for selection: Routine safety monitoring indicators for clinical trials of medical devices.

Definition: Serious adverse events are those that occur in the course of a clinical trial that result in death or serious deterioration of health, including fatal illness or injury, permanent defects in body structure or function, requiring hospitalization or prolonged hospital stay, or requiring medical or surgical intervention to avoid permanent defects in body structure or body function; Events that lead to fetal distress, fetal death, or congenital anomalies or birth defects.

Metric type: Qualitative.

Data collection time: the entire clinical trial cycle.

Evaluation time: 3 months \pm 7 days after the last treatment.

Evaluation methodology: The investigator recorded all SAEs that occurred.

Calculation formula: Serious adverse event rate = number of subjects with serious adverse events in this group / total number of subjects in this group \times 100%.

(6) Incidence of device defects

Reason for selection: Routine safety monitoring indicators for clinical trials of medical devices.

Definition of indicators: refers to the unreasonable risk that medical devices may endanger human health and life safety under normal use during clinical trials, such as crash.

Metric type: Qualitative.

Time of data collection: during treatment.

Evaluation time: After the last treatment was completed.

Evaluation methodology: The investigator recorded all device defects that occurred.

Calculation formula: incidence of device defects = number of occurrences of device defects / number of times of device use \times 100%.

4 Statistical considerations

